With respect to upper limb surgery, there was similar quality of pain relief with ropivacaine and bupivacaine in a trial conducted among patients who had interscalene block prior to major open surgeries to their shoulders (Borgeat *et al.*, 2001). However, the authors observed that the hand strength returned more expeditiously and the degree of paraesthesia at the finger level was less in patients receiving 0.2% ropivacaine than in those receiving 0.15% bupivacaine (Borgeat *et al.*, 2001). At 24 hours after the performance of interscalene block, the hand strength (the primary endpoint) was reduced

by 48% in 0.2% ropivacaine recipients and 66% in bupivacaine recipients (p value <0.05) (Borgeat *et al.*, 2001). Furthermore, the hand strength was completely recovered for subjects in ropivacaine arm at 6 hours following the cessation of ropivacaine infusion. In bupivacaine group, however, there was a protracted recovery of hand strength since it was still reduced by 25% after the end of bupivacaine administration and the difference was significant when comparison was made with the ropivacaine group (Borgeat *et al.*, 2001). Nevertheless, the results of this study should be taken with a pinch of salt due to the controversial use of the non-validated bulb-grip device test as a measurement tool for motor strength by the authors.

In another study conducted locally by Mageswaran and Choy (2010), subjects undergoing elective or orthopaedic upper limb surgery were randomized into receiving either 0.5% ropivacaine or 0.5% levobupivacaine via infraclavicular brachial plexus block. The mean onset for sensory and motor block were significantly higher in 0.5% ropivacaine recipients than 0.5 levobupivacaine recipients (sensory block: 13.5 minutes vs 11.1 minutes (p value = 0.003), motor block: 19.0 minutes vs 17.1 minutes (p value = 0.013). However, no statistically-significant difference was found with regard to the analgesic efficacy at 6 hours after the surgery. Again, the findings of this study should not be taken at face value and hence careful consideration should be exercised before recognising the validty of such results since the number of participants allocated in each intervention group was small (n = 24 per group). Hence, further studies are required to gain further information on the exact benefits of ropivacaine over other anaesthetic agents such as bupivacaine for upper limb surgeries.

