 - Motor blockade was also evaluated every 5 minutes up to 30 minutes following the completion of administration of intervention.
 - Motor block was assessed by subject's capability of flexing his / her elbow and hand against gravity. This was then graded according to the scale utilised by Borgeat, Ekatodramis and Durmont (2001).
 - Motor block success was considered achieved when the motor power was reduced to grade 3 or more based on the criteria used by Ammar and Mahmoud (2012).
- Intra-surgical assessment:
 - Requirement of block supplementation, surgical wound infiltration and patient requested sedation or general anaesthesia
 - Surgical anaesthesia success was defined as surgery without the requirements of block supplementation, general anesthesia (administered for incomplete block) or surgical site infiltration

- Haemodynamic monitoring was performed at baseline, after LA injection, after 15 min, 30 min, 1 hour of block procedure & after completing surgery.
- Postoperative assessment:
 - Sensory and motor blockade durations were assessed on half-hourly basis (up to 12 hours postoperatively), during the post surgical period.
 - Patient-controlled analgesia (PCA) morphine or IV tramadol was given as rescue analgesia.
 - Pain scores were assessed using the visual rating scale (VRS) (0-10) where pain was evaluated when the patients were resting at 1, 2, 4, 12, 24 hours postoperatively.
 - The duration of analgesia (time interval from the completion of local anesthetic administration until the first need of rescue analgesia in the form of PCA morphine or IV tramadol) and the amount of morphine or tramadol consumed during the postoperative 24 hours were also documented.
 - Any evidence of complications (e.g., bruises/swelling at the block site, chest pain/ breathing difficulty, dysaesthesia/ muscle weakness in the operated extremity not related to the site of operation) were also recorded.
 - Surgeons were alerted to report any neurological problems not related to surgery during the clinical rounds prior to the patients were discharged from the hospital.
 - Anaesthetic preferences (one of the following: 1) the BPB; 2) block under deep sedation; 3) block under GA).
 - Preferred block for future hand operations was then recorded.

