5.1 THE CLINICO-DEMOGRAPHIC PROFILES OF THE STUDY PARTICIPANTS

[figure not shown]
On the whole, 86 study participants were included in the analysis. The mean age and weight of the participants are similar between the two groups of interventions. Apart from that, both intervention groups exhibit similar patterns of VRS pain score, volumes of local anaesthetics received, supplemental local anaesthetics received and PCA morphine profiles.

With regards to gender and ethnic compositions, both intervention groups, in general, demonstrated similar proportions of females, males and each ethnic groups. Furthermore, both intervention arms have also relatively the same proportions of participants for each ASA grade. Nevertheless, with respect to the specific surgical sites, more study participants in the ropivacaine group had surgeries to their arms whilst more patients in the combined parecoxib-and-ropivacaine group had surgeries to their forearms. Besides, there are also two missing data in this group. However, it can be safely said that proportions of surgical sites are roughly similar in both groups. For further information, refer to table 5.1 and figures 5.1-5.3.

Parameters 1	Parecoxib + Ropi Mean (SD)	vacaine (n=43) n(%)	Ropiva Mean (SD)	caine (n=43) n(%)
Age	43.8 (13.7) 47.5 (26) ^a		46.3 (12.6) 51.0 (21.0) ^a	
Weight (kg)	60.8 (7.6) 60.0 (13.0) ^a		61.6 (7.6) 60.0 (12.0) ^a	
VRS pain score	1.0 (0)		1.0 (0)	
LA volume	20.0 (0)		20.0 (0)	
Supplement LA volume	0.0 (0)		0.0 (0)	
Time to 1 st PCA morphine (hours)	0.0 (0)		0.0 (0)	
PCA Morphine deman within 24 hours (count			0.0 (0)	
PCA Morphine given within 24 hours (count	0.0 (0) s)		0.0 (0)	
Gender Female Male		16 (37.2) 27 (62.8)		0 (46.5) 3 (53.5)
Ethnicity				
Malay Chinese Others		42 (97.7) 1 (2.3) 0 (0)	۷	41 (95.3) 1 (2.35) 1 (2.35)
Surgical sites Forearm Arm Hand Fingers Missing		14 (32.5) 21 (48.9) 0 (0) 6 (14.0) 2 (4.6)		$\begin{array}{cccc} 8 & (18.6) \\ 31 & (72.1) \\ 1 & (2.3) \\ 3 & (7.0) \\ 0 & (0) \end{array}$
ASA grades I II		7 (16.3) 36 (83.7)		6 (14.0) 37 (86.0)
Preoperative VRS scor ^a Median (Interquartile range			0.0 (0.0)	

Table 5.1: The clinico-demographic characteristics of study participants (n = 86)

^aMedian (Interquartile range)

[figure not shown]

Figure 5.1 (a-b): The proportions and percentages of subjects in each intervention arm, as stratified by gender and ethnicity of subjects

[figure not shown]

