It is a well-known fact that prostaglandin E2 (PGE₂) has the capacity to sensitize the peripheral nerve endings to pain (Warner and Mitchell 2004). This is substantiated by Svenson and Yaksh (2002) who had explicated in their excellent review article that the COX-2 enzyme could be indigenously found in the dorsal and ventral grey matter of the spine, dorsal root ganglia and even in the glial cell such as astrocytes. Apart from that, Beiche et al. (1998) also confirmed the presence of COX-2 using immunohistochemical techniques in the neurons that are located in the whole layers of spinal cord's lamina, especially in its outermost superficial layer. The presence of constitutive COX-2 in the neuronal cells of all lamina of the spinal cord may explain for the acute antinociceptive effect of the intrathecal administration of COX-2 inhibitors. Furthermore, Pinardi et al. (2005), together with the observations made Samad et al. (2001) and Seybold et al. (2001), further endorsed the conclusion drawn from the other studies that the COX-2induced prostanoid at the spinal level may result in the perpetuation of hyperalgesic state. These perhaps partly expound the abolition of hyperalgesic state induced by the substance P and the NMDA-mediated nociceptive transmission via cycloxygenase inhibition (Malmberg and Yaksh 1992) and carrageenan-induced thermal hyperalgesia by the COX-2-specific inhibitor that was intrathecally administered (Yaksh et al., 2001). In addition, Warner and Mitchell (2004) also stated that the induction of COX-2 expression and hence PGE₂ synthesis by the injured cells may in turn result in the neuronal hyperexcitability that will cause pain hypersensitivity in the neighbouring uninjured cells. Moreover, Ossipov *et al.* (2004) also established the presence of μ -opioid receptors in the same locality (i.e. the outermost laminae of the spinal cord's dorsal laminae) as COX-2 inhibitor. All these facts lend further support to the hypothesis that the combination of analgesic or anaesthetic agents with divergent mechanistic profiles may be more effective in attenuating acute pain and prolonging the effects of anaesthetic agents (Phillips and Currier 2004). The results of these prior research hence corroborated the outcomes of our study that the addition of parecoxib to other anaesthetic agents may further reduce the sensitization of nerve ending to pain and, in general, reinforce the duration of sensory and motor blockades.

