participants since we are not in possession of any valid apparatus that can establish the threshold of heat or pressure-induced pain in humans accurately. We did evaluate the preoperative VRS as a surrogate measure for the pain threshold of each study participant but we believe this is not an accurate measure of the participants' pain tolerance. Finally, we only employed a single dose of parecoxib (i.e. 20 mg parecoxib) and consequently we were not being able to evaluate the association between different doses of parecoxib and the trend in the duration and onset of sensory and motor blockade. However, we did ascertained that the inclusion of 20 mg parecoxib to ropivacaine increased the duration of motor and sensory blockades.

SECTION SEVEN

CONCLUSION

All in all, our conclusively demonstrated that the addition of parecoxib to ropivacaine prolonged the duration of sensory and motor blockades, but not their onset. Several mechanisms have been proposed that may explain the differential effects of parecoxib on both onset and duration of the blockades. Besides, we also discussed about a few limitations of our study and recommended several remedies to improve the designs and analyses of future trials addressing the same research question. Contigent upon the findings of future studies, a 20 mg adjunct parecoxib will provide better anaesthetic effects than a single 0.75% ropivacaine in patients undergoing upper limb surgeries.

REFERENCES

- Aberg G. Toxicological and local anaesthetic effects of optically active isomers of two local anaesthetic compounds. Acta Pharmacologica et Toxicologica 1972;31:273–286.

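### Timed postoperative pain, duration of analgesia and tramadol use go unreported, and PCA morphine is filed as a patient characteristic, yet reduced pain sensitization is credited to this trial

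*Combined protocol and SAP*

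**What the plan says.** **What was to be measured.** Under postoperative assessment, Section 4.10.2 states that "pain was evaluated when the patients were resting at 1, 2, 4, 12, 24 hours postoperatively". It adds that duration of analgesia (completion of the local anaesthetic injection to first need for rescue) and the morphine or tramadol consumed in 24 hours were documented. Section 4.9 defines time to first PCA, PCA volume, PCA demand and VRS among the other clinical variables. Time to first PCA and PCA demand are defined there as strictly positive.

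**What was reported.** Table 5.1, the table of patient characteristics, contains a VRS pain score row, supplemental local anaesthetic, and three PCA morphine rows. Section 5.1 says that the arms show "similar patterns of VRS pain score, volumes of local anaesthetics received, supplemental local anaesthetics received and PCA morphine profiles". Tables 5.4 and 5.5, which hold the between-arm comparisons, have no pain or rescue row.

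**What was concluded.** Section 6.2 says earlier research corroborates the "outcomes of our study that the addition of parecoxib to other anaesthetic agents may further reduce the sensitization of nerve ending to pain". Section Seven closes by saying, conditionally on the findings of future studies, that "a 20 mg adjunct parecoxib will provide better anaesthetic effects than a single 0.75% ropivacaine".

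**The concern.** Rescue morphine use is measured after treatment. It cannot show that the groups were alike at entry, and placing it in the characteristics table removes it from the comparison a reader most wants to see. The timed pain scores and duration of analgesia are the direct evidence on whether a longer block gave better pain relief, and they are missing.

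The direction cannot be assumed from the block result. Section 2.4 describes two earlier trials of adjunct parecoxib. The axillary-block trial found lower pain scores. In the infraclavicular-block trial, parecoxib was numerically worse than saline for day-1 pain (2.68 against 2.11) and for time to first analgesic (1248 against 1408 minutes). A statement that this trial's outcomes show less pain sensitization therefore needs this trial's own pain data.

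**Working it through.** **1. The block-duration results reproduce.** Inputs are from Table 5.4, with n = 43 per arm.
- Motor block: 4.84 (SD 0.77) against 3.86 (SD 0.60) hours. SE = √(0.77²/43 + 0.60²/43) = 0.149. With the printed difference of 0.97, t = 6.52 and the 95% CI is 0.67 to 1.27. With 0.98, the difference of the rounded means, t = 6.58 and the CI is 0.68 to 1.28. Welch df = 79.3. The report prints t = 6.561, df 79.342 and CI 0.68 to 1.27, which agrees within rounding.
- Sensory block: U = 199. z = (199 − 43·43/2)/√(43·43·87/12) = −725.5/115.8 = −6.27, p ≈ 4 × 10⁻¹⁰, consistent with the printed p < 0.001.

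**2. Planned measures against reported results.**

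| Measure (Section 4.10.2) | Where reported |
|---|---|
| Resting VRS at 1, 2, 4, 12, 24 h | Nowhere by time point |
| Duration of analgesia | Nowhere |
| Tramadol in 24 h | Nowhere |
| Morphine in 24 h | Table 5.1 only, no between-arm comparison |

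The captioned figures in Section 5 concern demographics, ASA grade, surgical site, and block onset, completeness and duration.

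**3. What the PCA rows can mean.** Time to first PCA is 0.0 (0) hours in both arms, and PCA morphine given is 0.0 (0) in both. For demand, one cell is 0.0 (0) and the other is not legible in the available text. Read literally, a time of 0.0 hours with SD 0 means every patient received morphine the moment surgery ended, while 0.0 given means that none did. A patient who never used PCA has no time to first dose, so zero is the wrong entry for that case. Zeros also conflict with the strictly positive definitions in Section 4.9. They may be a code for not used or not recorded.

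**4. The most favourable reading of the zeros.** Assume they mean 0/43 users in each arm.
- Wilson upper limit per arm: 1.96²/(43 + 1.96²) = 3.84/46.84 = 8.2%. The exact limit, 1 − 0.025^(1/43), is also 8.2%.
- Newcombe 95% CI for the difference: 0 ± 8.2 percentage points.

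This covers morphine by PCA only. With SD 0 in both arms, no test of the means can be computed.

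**5. What the VRS row can mean.** It reads 1.0 (0) in both arms with no time point. It is not baseline pain, because Table 5.1 has a separate preoperative VRS row. It is followed by local anaesthetic volume and supplement volume, the same order as the block-technique items in the case report form, where the pain item is procedure-related pain. Section 4.10.2 scores that immediately after the needle is removed. The form's scale runs from 1 to 10 and Section 4.10.2's from 0 to 10, so on the form's scale 1.0 (0) is the floor. The row is probably needle pain and says nothing about postoperative analgesia.

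**The case against.** The strongest reply is that the conclusions are mostly about block, and block is what was studied. The five specific objectives and Table 4.1 list only block outcomes, while pain and PCA are classed as other variables. The closing sentence of Section Seven is conditional on future studies, anaesthetic most naturally refers to block rather than pain relief, and the section opens with what was shown: longer duration, no change in onset. The abstract's conclusion is confined to block results. The sentence in Section 6.2 says may, and it ends with block duration. All of this stands, and it limits the point to incomplete secondary reporting and one unsupported attribution.

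Three stronger readings are tempting, and the documents do not support them.
- *Rescue analgesia and pain were identical in both arms, so the trial shows no analgesic benefit.* The zeros may be codes, one cell is unreadable, tramadol is absent, and the VRS row is probably procedural. The published rows are uninformative, which differs from showing no difference.
- *The variables were ignored.* Section 5.1 does report them as similar. They are misclassified and then left out of the interpretation.
- *Longer motor block is wrongly counted as a benefit, because Section 2.2.3 values that* "the hand strength returned more expeditiously" *with one drug.* That passage concerns interscalene block with infusions of different drugs, and the authors themselves advise caution about it. Motor block duration was a stated objective here, and the documents do not settle whether another hour is desirable.

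What the reply does not answer is the missing timed VRS, duration of analgesia and tramadol data, the use of post-treatment PCA rows as evidence of similarity, and the claim in Section 6.2 of a pain outcome that is nowhere reported.

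**Conclusion.** The point holds as a reporting and interpretation fault. Three measures described as collected have no reported result, and a fourth, PCA morphine, sits in the wrong table with values that cannot all be literal. No reported result supports reduced sensitization to pain as an outcome of this trial. On the most favourable reading, PCA use is 0/43 against 0/43 with an interval of about ±8.2 points, and this rests on the assumption that zero means no use. The primary findings are unaffected: longer sensory block (1.5 h) and motor block (0.97 h) reproduce or are consistent with the printed statistics.

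Two assumptions matter. That the data exist rests on Section 4.10.2, since I have not seen the postoperative pages of the case report form. That the VRS row is procedural pain is an inference from the order of items.

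**What to change.** - Move the PCA rows from Table 5.1 to a table of secondary outcomes. Report by arm, with between-arm differences and 95% intervals: VRS at each of the five times, duration of analgesia, and morphine and tramadol use (number of users and amount). Treat patients who needed no rescue as censored for duration of analgesia, not as zero.
- State the time point of the VRS row in Table 5.1, and explain what the zeros in the PCA rows mean.
- In Section 6.2, remove the attribution of reduced pain sensitization to this study's outcomes. The mechanism can stay as a hypothesis from earlier work.
- In Section Seven, replace the phrase about better anaesthetic effects with wording such as: *Adding parecoxib lengthened sensory and motor block. This report presents no postoperative pain or rescue comparison from which an analgesic benefit can be concluded.* Update the second sentence once the data are tabulated.
- Leave the abstract's conclusion as it is.

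The cost is a modest amount of tabulation of data described as already collected, and a narrower closing claim.

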- Zeilhofer HU. The glycinergic control of spinal pain processing. Cellular and Molecular Life Sciences 2005;62(18):2027-35.

CASE REPORT FORM (CRF)

CASE NO

GROUP: SCB / ICB

DATA COLLECTION SHEET: EFFECT OF PARECOXIB 20MG AS AN ADJUNCT IN 0.75% ROPIVACAINE TO ULTRASOUND GUIDED SUPRACLAVICULAR BLOCK FOR UPPER LIMB SURGERY

PRE OP SCREENING:			
INCLUSION CRITERIA	TICK (√)	EXCLUSION CRITERIA	(X)
Adult (age 18 to 60)		Patient refusal for BPB	
ASA I to II		Known case of allergic to parecoxib and local anesthesia	
Expected duration of surgery 1-4 hours		History of previous brachial plexus injury	
		Pregnancy	
		History of chronic pain, those that using chronic analgesic medication	
		Coagulapathy	
		Systemic infection or local infection at site of injection	
		History of Ischaemic Heart Disease.	
		History of Renal failure	
		History of Atopy	

BACKGROUND DATA

Date:

Full Surgical Procedure:

SITE OF SURGERY	CODING	TICK ($$)	
Arm	1		
Forearm	2		
Hand	3		
Fingers	4		
R/N: Sex: M/H			
Age: Sex: M/F	F E	Ethnicity: M / C	/I /Others
ASA: I / II			
If ASA II, state the disease/s Height: cm Weight: _			
	k	g	
BLOCK TECHNIQUE	100		
• Size of the needle: 50 / 80/			
• Depth of skin to superior pa			
• VRS of procedure-related p	aın (1 to 10)	:	
• Volume of LA given:	ml		
• Supplement volume of LA	given:	ml	
• Time of completing LA inje	ection:		
• Time of sensory block onset (reduce sensation ≤ 25% from contralateral side):			
Onset of sensory block:	mi	n	
• Time of motor block onset	(reduce mot	or power $\leq 25\%$	from contralateral side):
Onset of motor block:	min		

• Assessment of sensory block after 30 min:

SENSORY BLOCK	TICK ($$)
2 (Normal)	
1 (partial block/ reduced)	
0 (Complete block/ absent)	

• Assessment of motor block after 30 min:

GRADE	TICK ($$)
1 (able to flex or extend the forearm)	
2 (able to flex or extend only the wrist	
and fingers)	
3 (able to flex or extend only the	
fingers)	
4 (unable to move the forearm, wrist,	
and fingers)	

QUALITY OF OPERATIVE CONDITIONS

QUALITY OF OP	Please tick ($$)
4 (Excellent/ No complaint from patient)	
3 (Good/ Minor complaint with no need for the	
supplemental analgesics)	
2 (Moderate/ Complaint that required supplemental	
analgesia)	
1(Unsuccessful/ Patient given general anaesthesia)	

SITE REQUIRED SUPPLEMENT BLOCK

PATCHY BLOCK SITE	Please tick ($$)
